7.2. Biomarker Data Management

Data generated by analytical laboratories will be delivered through secure FTP or through the best practices of the industry to ensure high level data protection. The data received will be stored in the sponsor's secure server.

Data QC document from each analytical laboratory will be delivered to the project team and stored in the sponsor's secure server. Additional QC will be performed by the computational biology team, and the QC methods will be defined in the supplemental statistical analysis plan.

7.3. Handling of Missing Values

Assayed values that are below the lower limit of quantification (LLOQ) will be set to LLOQ. Imputation will not be performed in the case of missing values.

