#### **1.1.3.4. Trans-differentiation as a Mechanism of AR Resistance**

Emerging data now suggests that tumors can evade AR modulators by trans-differentiation into a neuroendocrine like phenotype that is characterized by mutations that include loss of RB, p53, or PTEN, and an increase in copy number of N-MYC genes. These neuroendocrine prostate cancer (NEPC) tumors are thought to transdifferentiate from a CRPC luminal adenocarcinoma cell by divergent clonal evolution. Additionally, NEPCs are often characterized by loss of AR expression and are hormone refractory. This is an especially aggressive form of prostate cancer with a survival of approximately 1 year. In a recent report of 114 metastatic biopsies, tumors progressing on enzalutamide or abiraterone were found to have neuroendocrine like features, including lower AR expression levels and loss of RB and p53. Epigenetic reprogramming involving the histone methyltransferase enhancer of zeste homolog 2 (EZH2) has also been implicated in driving neuroendocrine prostate cancer, suggesting that novel agents such as EZH2 inhibitors may have utility in this setting.

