
AR inhibition:
 
 
To evaluate AR gene alterations as mechanisms of resistance to enzalutamide or abiraterone;
 
To evaluate changes in expression of nuclear hormone receptor genes as a mechanism of resistance to enzalutamide or abiraterone.
 
	
 
Change in the frequency of AR gene alterations between pre-treatment archival and post-progression samples;
 
The frequency of AR gene alterations in cfDNA;
 
Changes in the expression of nuclear hormone receptors or related RNA signatures reflecting nuclear receptor pathway activity between pre-treatment archival and post-progression samples.
 

PARP inhibition:
 
 
To evaluate somatic reversion of germline BRCA (gBRCA) gene alterations as a mechanism of resistance to monotherapy PARP inhibition.
 
	
 
Change in the frequency of somatic reversion alterations in gBRCA mutant allele between pre-treatment archival and post-progression samples.
 

CCI
 
 
CCI
 
	
CCI

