2.3. Biomarker Study Objectives

Table 1 Study Objectives

| |
|---|
| Primary Objective: |
| 
 • To obtain and analyze archival pre-treatment tumor samples and post-progression tumor biopsies to identify molecular markers of resistance to selected anti-cancer therapies. |
| Secondary Objectives: |
| 
 • To evaluate the success rate in obtaining paired archival and post-progression tumor biopsies that are adequate to meet the objectives of the study; • To determine concordance in gene alterations identified by NGS analysis of post-progression tumor tissue and blood. |
| Secondary Objectives by Target Biology:* |
| PD-1/-L1 inhibition: |
| 
 • To evaluate alterations in genes encoding HLA, β2-Microglobulin, Signal transducer and activator of transcription 1 (STAT1), JAK1, JAK2, IFN-γ, and interferon-gamma receptor (IFNGR) as mechanisms of resistance to PD-1/PD-L1 checkpoint blockade. |
| CDK4/6 inhibition: |
| 
 • To evaluate alterations in the Rb gene as a mechanism of resistance to palbociclib. |
| AR inhibition: |
| 
 • To evaluate AR gene alterations as mechanisms of resistance to enzalutamide or abiraterone; • To evaluate changes in expression of nuclear hormone receptor genes as a mechanism of resistance to enzalutamide or abiraterone. |
| PARP inhibition: |
| 
 • To evaluate somatic reversion of germline BRCA (gBRCA) gene alterations as a mechanism of resistance to monotherapy PARP inhibition. |
| CCI |
| |
| |
| |
| |

*All abbreviations are explained in the Appendix 1 of study protocol.

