6. ENDPOINTS AND COVARIATES

6.1. Endpoints

Table 2 Primary, Secondary and Exploratory Endpoints

| |
|--|
| Primary Endpoint: |
| 
 Change in the frequency of gene alterations between pre-treatment tumor samples and post-progression tumor biopsies. |
| Secondary Endpoints: |
| 
 Proportion of patients with fully evaluable archival and post-progression tumor biopsy (eg, sample sufficient for all intended analyses at all measured time points); Overall agreement rates of gene alterations between post-progression biopsy tissue and blood NGS results. |
| Secondary Endpoints by Target Biology:* |
| PD-1/L1 inhibition: |
| 
 Change in the frequency of alterations in genes encoding HLA, β2-Microglobulin, STAT1, JAK1, JAK2, IFN-γ and IFN-γR between pre-treatment archival and post-progression samples; The frequency of alterations in genes encoding HLA, β2-Microglobulin, STAT1, JAK1, JAK2, IFN-γ and IFNGR in cfDNA. |
| CDK4/6 inhibition: |
| 
 Change in the frequency of RB1 gene alterations between pre-treatment archival and post-progression samples. The frequency of RB1 gene alterations in cfDNA and tumor tissue. |
| AR inhibition: |
| 
 Change in the frequency of AR gene alterations between pre-treatment archival and post-progression samples; The frequency of AR gene alterations in cfDNA and tumor tissue; Changes in the expression of nuclear hormone receptors or related RNA signatures reflecting nuclear receptor pathway activity between pre-treatment archival and post-progression samples. |
| PARP inhibition: |
| 
 Change in the frequency of somatic reversion alterations in gBRCA mutant allele between pre-treatment archival and post-progression samples. |
| CCI |
|  |

*All abbreviations are explained in the Appendix 1 of study protocol.

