8. STATISTICAL METHODOLOGY AND STATISTICAL ANALYSES

8.1. Statistical Methods

8.1.1. Statistical Methods for Continuous Variables

For the continuous variables, summary statistics including mean, min, max, quartiles, and 95% confidence intervals (CIs) of the mean will be reported per tumor type and cohort. For the continuous variables that are measured from two samples from the same subject, change between the two samples will be calculated. Summary statistics including mean, min, max, quartiles and 95% CIs of the change will be calculated for each cohort. As appropriate paired t test (or non-parametric equivalent) will be performed for the change and p values will be reported. For high dimensional data such as WES, RNASeq, Gene panel etc., a false discovery rate (FDR) based method (qvalue package in R or proc multtest in SAS) will be used for multiplicity adjustment (Storey, 2015).³

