| 
 • AR inhibition. | 
 • Change in the frequency of AR gene alterations between pre-treatment archival and post-progression samples. • The frequency of AR gene alterations in cfDNA, and tumor tissue. • Changes in the expression of nuclear hormone receptors or related RNA signatures reflecting nuclear receptor pathway activity between pre-treatment archival and post-progression samples. | 
 • For each alteration in cfDNA, the estimate of the frequency and the 95% CI at pre-treatment archival and post-progression will be generated. A score based 95% CI will be generated for the difference in frequency between pre-treatment archival and post-progression samples. • For each alteration, the estimate of the frequency and the 95% CI will be generated. • Estimates of mean expression and 95% CIs at pre-treatment archival and post progression will be generated; Estimates of the difference in expression and the 95% CI between pre-treatment archival and post-progression samples will be generated. P values will also be reported. |
| 
 • PARP inhibition. | 
 • Change in the frequency of somatic reversion alterations in gBRCA mutant allele between pre-treatment archival and post-progression samples. | 
 • For each somatic reversion alteration, the estimate of the frequency and the 95% CI at pre-treatment archival and post-progression will be generated. A score based 95% CI will be generated for the difference in frequency between pre-treatment archival and post-progression samples. |

CCI

CCI

CCI

CCI

CCI

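### Setting every value below the LLOQ to the LLOQ truncates falls in receptor expression, so the paired mean change in the AR cohorts can be distorted by an amount the documents do not let the reader bound

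*SAP*

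**What the plan says.** SAP 7.3 states "Assayed values that are below the lower limit of quantification (LLOQ) will be set to LLOQ" and then "Imputation will not be performed in the case of missing values". Neither sentence is limited to particular assays. SAP 7.1 lists two RNA platforms, a 2560-transcript targeted panel and whole-transcriptome sequencing, and gives an LLOQ for neither.

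The AR-inhibition endpoint in SAP 6.1 is "Changes in the expression of nuclear hormone receptors or related RNA signatures reflecting nuclear receptor pathway activity between pre-treatment archival and post-progression samples". The matching objective in SAP 2.3 is "To evaluate changes in expression of nuclear hormone receptor genes as a mechanism of resistance to enzalutamide or abiraterone". Neither specifies a direction.

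For the analysis, Table 3 in SAP 8.2.3 calls for mean expression with a 95% CI at each time point, and then: "Estimates of the difference in expression and the 95% CI between pre-treatment archival and post-progression samples will be generated. P values will also be reported". SAP 8.1.1 adds quartiles, minimum and maximum of the change, and "As appropriate paired t test (or non-parametric equivalent) will be performed for the change and p values will be reported".

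On biology, Protocol 1.1.3.4 says of neuroendocrine prostate cancers that "NEPCs are often characterized by loss of AR expression and are hormone refractory". Protocol 1.1.3.3 describes a mechanism in the other direction, increased expression of AR splice variants. Protocol Table 1 plans 50 evaluable patients in each of Cohorts 5 and 6.

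**The concern.** Replacing a value below the LLOQ by the LLOQ gives it the highest value it could have had. A patient whose receptor expression drops to unquantifiable is recorded with a fall that stops at the LLOQ. A patient below the LLOQ at both time points is recorded with a change of exactly zero. These values then enter a paired mean difference and its CI.

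Loss of expression is one of the signals this endpoint should be able to show, and it is the signal on which censoring acts most. At stake are the centre of the interval, its width (substitution also shrinks the SD of the change) and, if some tumours gain expression while others lose it, the sign of the reported mean change.

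**Working it through.** The documents give no LLOQ, SD or expected change for this endpoint, so there is no planned figure to reproduce. All numerical inputs below are assumptions except n = 50.

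**Step 1: direction for a single pair.** Write L for the LLOQ, x for the archival value and y for the post-progression value. The rule replaces the change y − x by max(y, L) − max(x, L). This can shrink a change or leave it alone; it cannot enlarge or reverse it (no violation in 1,000,000 simulated pairs). What happens to the cohort mean depends on which changes are shrunk.

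**Step 2: losses only.** Assume a log2 scale, archival mean 8 and SD 1.2, and y = x + shift + noise with noise SD 0.8. The shift is −δ in 15% of patients and 0 in the rest. The true mean change is −0.15δ. The post-progression SD within each group is √(1.2² + 0.8²) = 1.442. For a normal variable with mean m and SD s,

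E[max(X, L)] = L + (m − L)Φ(z) + sφ(z), z = (m − L)/s.

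Worked case, δ = 6 and L = 5:
- archival: 5 + 3(0.9938) + 1.2(0.0175) = 8.002
- post-progression, no loss: 5 + 3(0.9812) + 1.442(0.0459) = 8.010
- post-progression, loss: 5 − 3(0.0188) + 1.442(0.0459) = 5.010
- mean change: 0.85(8.010) + 0.15(5.010) − 8.002 = −0.44, against a true −0.90, so 49% is retained.

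Share of the true mean change retained, by the same formula:

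| Loss δ | True change | L = 3 | L = 4 | L = 5 | L = 6 |
|---|---|---|---|---|---|
| 2 | −0.30 | 99% | 97% | 88% | 64% |
| 3 | −0.45 | 98% | 93% | 79% | 55% |
| 6 | −0.90 | 80% | 66% | 49% | 31% |

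If no value lies below L, 100% is retained.

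For δ = 6 and n = 50, simulation gives these results at L = 3, 4, 5 and 6:
- The SD of the change falls to 83%, 72%, 60% and 48% of its true value.
- Coverage of the true mean by the nominal 95% CI falls from about 94% to about 86%, 70%, 38% and 5%.
- Paired-t power falls from about 0.85 to about 0.80, 0.74, 0.63 and 0.39.

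At L = 3 or 4 fewer than 0.1% of archival values are below L, so archival counts alone would not reveal the problem.

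**Step 3: losses and gains together.** Use a second assumed set: between-patient SD 1.5, within-sample SD 0.5, 15% of patients losing 4 units and 30% gaining 2. The true mean is 0.15(−4) + 0.30(2) = 0. With the LLOQ at the 1st, 5th and 20th percentile of archival values, the substituted mean is +0.12, +0.22 and +0.33. The paired-t rejection rate rises from about 0.05 to 0.09, 0.17 and 0.40. Here the mean moves away from zero.

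**Step 4: candidate remedies, in the Step 2 setting with δ = 6.**
- A left-censored normal model gives about −0.54 to −0.59 at L = 5 (substitution −0.44, truth −0.90) and −0.42 to −0.46 at L = 6 (substitution −0.28). It removes part of the bias. A subgroup with loss is a mixture, which one normal distribution does not describe.
- A signed-rank test has power of about 0.35 to 0.37 at L = 5 and 0.27 at L = 6. This is below the t test after substitution (0.61 to 0.63 and 0.38 to 0.42).
- An exact McNemar test on crossings of the LLOQ has power of about 0.79 at L = 5 and 6. It is weaker when L is low, because fewer losses cross. Six one-directional crossings are needed, since 2(½)⁶ = 0.031 but 2(½)⁵ = 0.0625. At L = 3 the chance of a crossing is about 0.15 × Φ(1/1.442) = 0.15 × 0.756 = 0.113. The power is then P(Bin(50, 0.113) ≥ 6), about 0.51, against 0.80 for the t test. Crossings therefore supplement the mean change and do not replace it.

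**The case against.** A reader might infer that loss of expression is what this endpoint looks for, and that the mean change is therefore biased toward zero. The documents do not support that. The endpoint and objective are non-directional, Protocol 1.1.3.3 cites increased splice-variant expression, and Step 3 shows the bias can run away from zero.

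It can also be said that the rule may never bite. It is one generic sentence, no LLOQ is reported for either RNA platform, and platform-specific QC is left to laboratory reports and a supplemental plan that is not available here. This stands: the effect may be nil. It does not excuse the gap, because as written the rule covers RNA data.

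The 6-unit case is severe, a 64-fold fall (2⁶) in bulk tissue, while Protocol 1.1.3.4 also speaks of lower, not only absent, AR expression. This stands too, and it is why the 2-unit and 3-unit rows are shown.

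SAP 8.1.1 already allows a non-parametric test and reports quartiles of the change. That helps the description, but the mean difference and CI in 8.2.3 would still use substituted values.

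Finally, this is a cohort-specific secondary endpoint, SAP 4.1 plans no formal hypothesis testing, and no decision rule depends on it. That limits the consequences, but the interval would still be published as an estimate.

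**Conclusion.** The concern holds in a conditional form. SAP 7.3 applies to RNA expression as written. Wherever post-progression values fall below the LLOQ, it truncates falls in an endpoint summarised by a paired mean and CI. The mean is attenuated if losses dominate and shifted upward if directions are mixed. A general claim of bias toward zero, or a flat statement that the study will understate loss of AR expression, goes further than the documents allow.

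The size runs from nil, if nothing is below the LLOQ, to large. Under the Step 2 assumptions, 99% to 64% of the true change is retained for a 2-unit loss and 80% to 31% for a 6-unit loss. These figures rest on assumed means, SDs, LLOQs and a 15% share of patients losing expression, none of which is in the documents. Redacted SAP text and the supplemental plan could not be checked.

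**What to change.** In SAP 7.3 and 8.1.1:
- Flag values below the LLOQ as left-censored, and state the LLOQ for each RNA platform or say that none applies.
- For each receptor and cohort, report the number below the LLOQ at each time point and the net proportion of patients moving from above to below it. Use the matched-pair score CI and McNemar test already specified in 8.1.2.
- When any value is below the LLOQ, add a left-censored estimate of the paired change as a sensitivity analysis beside the substituted mean.
- Do not replace the t test with a rank test as the remedy; in Step 4 it had less power than the t test after substitution.

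The cost is SAP wording and modest programming, with no new data. Protocol section 8 requires an amendment only for major changes to the primary endpoint or its analysis, so none should be needed. The drawback is the distributional assumption in the censored model, which removes only part of the bias when a subgroup loses expression. The crossing counts should be read alongside it.

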8. STATISTICAL METHODOLOGY AND STATISTICAL ANALYSES

8.1. Statistical Methods

8.1.1. Statistical Methods for Continuous Variables

For the continuous variables, summary statistics including mean, min, max, quartiles, and 95% confidence intervals (CIs) of the mean will be reported per tumor type and cohort. For the continuous variables that are measured from two samples from the same subject, change between the two samples will be calculated. Summary statistics including mean, min, max, quartiles and 95% CIs of the change will be calculated for each cohort. As appropriate paired t test (or non-parametric equivalent) will be performed for the change and p values will be reported. For high dimensional data such as WES, RNASeq, Gene panel etc., a false discovery rate (FDR) based method (qvalue package in R or proc multtest in SAS) will be used for multiplicity adjustment (Storey, 2015).³

8.1.2. Statistical Methods for Categorical Variables

Regular Wald CIs suffer from low coverage probabilities that may be below nominal level. An improved CI estimation for the difference of proportions between matched pair will be employed (Agresti and Min, 2005; Tango 1998).^{1,4}

For n matched pairs on a binary response, denote the probability of outcome i for the first observation and outcome j for the second observation by π_{ij} , where outcome 1 = 'positive' and 2 = 'negative'. Denote the four corresponding sample proportions by $p_{11} = a/N$, $p_{12} = b/N$, $p_{21} = c/N$, and $p_{22} = d/N$. Let $\pi_1 = \pi_{11} + \pi_{12}$, $\pi_2 = \pi_{21} + \pi_{22}$. Denote the sample proportions of positives by p_1 and p_2 , $p_1 = p_{11} + p_{12}$, $p_2 = p_{21} + p_{22}$. Notations are illustrated in the table below:

| | Positive | Negative | Total |
|----------|---------------|--------------|---------------|
| Positive | $a (p_{11})$ | $b (p_{12})$ | $a + b (p_1)$ |
| Negative | $c (p_{21})$ | $d (p_{22})$ | $c + d$ |
| Total | $a + c (p_2)$ | $b + d$ | N |

For the matched pairs, the score interval consists of the set of $\Delta = \pi_1 - \pi_2$ values for which

$$\frac{|(p_2 - p_1) - \Delta|}{\sqrt{[(\hat{\pi}_{12}(\Delta) + \hat{\pi}_{21}(\Delta)) - \Delta^2]/n}} < z_{\alpha/2}$$

where $\pi_{jk}(\Delta)$ denotes the ML estimate of π_{jk} under the constraint that $\pi_1 - \pi_2 = \Delta$. There is not a closed-form expression for the resulting interval, but it can be obtained using iterative methods. The iteration stops when the score is close to $Z\alpha/2$ within defined margin 1e-06. The calculation of the score based interval can be performed with function scoreci.mp() in R package PropCIs or equivalent SAS macro program. McNemar test (mcnemar.test() in R or proc freq in SAS) will be used to compare the proportions between archival and de novo samples, and p values will be reported. For high dimensional data such as WES, RNASeq,

Gene panel etc., an FDR based method (qvalue package in R or proc multtest in SAS) may be used for multiplicity adjustment (Storey, 2015).³

For the CI estimation of proportion from one sample, Wilson score method will be used (Wilson, 1927). The calculation of the score based interval can be performed with function scoreci in R package PropCIs or proc freq in SAS.

$$\frac{\hat{p} + \frac{z^2}{2n}}{1 + \frac{z^2}{n}} \pm \frac{z}{1 + \frac{z^2}{n}} \sqrt{\frac{\hat{p}(1 - \hat{p})}{n} + \frac{z^2}{4n^2}}$$

Assessment of agreement between two samples on a categorical endpoint can be calculated using Cohen's kappa (Cohen, 1960) in Proc Freq.²

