### 8.5. Analysis of Other Endpoints

#### 8.5.1. Analysis of Primary Endpoint

The primary endpoint is the change in the frequency of gene alterations associated with disease progression. As the goal is to compare the differences in frequency of mutation rate between pre-treatment archival and post-progression samples, a score based 95% CI for matched pairs will be calculated for each genomic alteration. Estimates of the frequency of mutations, the difference of the frequency of mutations between archival and post-progression samples and associated 95% CIs will be generated.

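### SAP 8.1.2 prints an incorrect matched-pairs score interval: the second proportion is misdefined and Δ runs opposite to its estimate, so a program coded from the text does not return the intended interval

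*SAP*

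**What the plan says.** Protocol 8.5.1 says that "a score based 95% CI for matched pairs will be calculated for each genomic alteration" and cites two published methods for paired proportions. SAP 8.1.2 cites the same two and writes the method out. Index 1 is positive and index 2 is negative; the first index belongs to the first observation and the second index to the second.

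- Text: "Denote the sample proportions of positives by p_1 and p_2", then p1 = p11 + p12 and p2 = p21 + p22, with π1 and π2 built the same way.
- Notation table: p2 is the first column total, a + c, over N. Rows and columns carry only positive and negative, not archival or de novo.
- Interval: "For the matched pairs, the score interval consists of the set of" Δ = π1 − π2 at which |(p2 − p1) − Δ|, divided by a standard error, is below the normal quantile. The standard error uses maximum likelihood estimates constrained by π1 − π2 = Δ.
- Software: "The calculation of the score based interval can be performed with function scoreci.mp() in R package PropCIs or equivalent SAS macro program".

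SAP 8.2.1 sends the primary endpoint to this section, and SAP 8.2.3 sends the asset-specific secondary endpoints there.

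**The concern.** Cells 21 and 22 together are the patients negative on the first observation, so the text's p2 equals 1 − p1. It is not a proportion of positives and carries nothing about the second sample. It also contradicts the table in the same section.

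Separately, the estimate p2 − p1 is compared with a Δ that means π1 − π2. Near the estimate, the constrained likelihood is therefore asked to fit a change of the same size in the opposite direction, and the resulting variance is too large whenever gains and losses are unequal.

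At stake are the confidence limits on the primary endpoint and on every paired-frequency secondary endpoint, if someone programs or double-programs from the printed formula. That program would disagree with the R function and with Protocol Table 2.

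**Working it through.** **Inputs.** Two-sided 95%, z = 1.960 (Protocol 8.5.1). Sample sizes 50, 75 and 100 and observed changes of 10%, 20% and 30% (Protocol Table 2). With the first observation taken as archival and the second as de novo, b counts losses (cell 12) and c counts gains (cell 21). Table 2 does not state the discordant cells. I assume b = 0 and c = n × difference; b = 1 or 2 does not fit all rows.

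**Formula.** Let θ = π21 − π12. The constrained estimate x of π12 is the larger root of

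2n·x² + [(2n − c + b)θ − b − c]·x − bθ(1 − θ) = 0,

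floored so that no cell is negative. The variance term is (2x + θ − θ²)/n. The limits solve [(c − b)/n − Δ]² = z² × variance. The intended method has θ = Δ. The printed constraint with the table's p2 has θ = −Δ.

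**One row by hand: n = 100, c = 10, b = 0, z²/n = 0.038415.**

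- Intended: x = (10 − 190Δ)/200, which is 0 once Δ ≥ 10/190 = 0.0526. Both limits lie above that, so (0.10 − Δ)² = 0.038415·Δ(1 − Δ), or 1.038415Δ² − 0.238415Δ + 0.01 = 0. Roots: 5.5% and 17.4%. Table 2 gives 6% and 17%.
- As printed: x = (10 + 190Δ)/200, so the variance term times n is 0.10 + 0.90Δ − Δ². Then 1.038415Δ² − 0.234573Δ + 0.006159 = 0. Roots: 3.0% and 19.6%.

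At Δ = p̂ with no losses, the intended term is p̂(1 − p̂) and the printed one is p̂ + (1 − p̂)p̂ − p̂² = 2p̂(1 − p̂). The variance doubles there, and √2 = 1.41 explains why most rows come out about 40% too wide.

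**All Table 2 rows (b = 0, in %).**

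| n | Change | Table 2 | Intended | Printed signs, table's p2 | Excess width |
|---|---|---|---|---|---|
| 100 | 10 | 6, 17 | 5.5, 17.4 | 3.0, 19.6 | 39% |
| 100 | 20 | 13, 29 | 13.3, 28.9 | 9.8, 31.6 | 40% |
| 100 | 30 | 22, 40 | 21.9, 39.6 | 17.7, 42.7 | 41% |
| 75 | 10 | 5, 19 | 4.6, 18.9 | 2.2, 21.2 | 34% |
| 75 | 20 | 13, 30 | 12.5, 30.4 | 8.5, 33.5 | 40% |
| 75 | 30 | 21, 41 | 20.8, 41.1 | 15.9, 44.6 | 41% |
| 50 | 10 | 2, 21 | 2.2, 21.4 | 0.9, 24.1 | 21% |
| 50 | 20 | 11, 33 | 11.2, 33.0 | 6.3, 36.6 | 39% |
| 50 | 30 | 19, 44 | 19.1, 43.8 | 13.0, 47.7 | 40% |

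The intended method matches nine of nine rows and the printed signs match none. The 10% and 30% rows at n = 75 needed 7.5 and 22.5 patients.

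**With losses.**

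| n | Gains / losses | Intended | Printed signs | Excess width |
|---|---|---|---|---|
| 100 | 12 / 2 | 3.1, 18.2 | 2.3, 20.0 | 17% |
| 100 | 15 / 5 | 1.3, 19.2 | 1.1, 20.7 | 9% |
| 100 | 20 / 10 | −0.8, 20.8 | −0.7, 21.8 | 4% |
| 100 | 8 / 5 | −4.5, 10.9 | −4.1, 11.5 | 1% |
| 100 | 8 / 8 | −8.4, 8.4 | −8.4, 8.4 | 0% |

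**The text's p2.** The estimate becomes (1 − p1) − p1 = 1 − 2p1. With 20% positive in the archival sample it is 60%, whatever the de novo sample shows. With the text's π2 as well and the printed signs, no Δ satisfies the inequality at n = 100, c = 10 when a/n is 0, 0.05 or 0.20. At a/n = 0.40 the result is 15.8% to 22.4%, where the intended interval is 5.5% to 17.4%.

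**The case against.** The printed formula is not the sole specification. Both documents cite the source methods, the SAP names a specific R function, and its wording requires any SAS macro to be equivalent to that function. A macro that disagreed with it would already fail the SAP. This stands: with the named function, assuming it implements the cited method, no reported interval changes.

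The p2 slip is contradicted by the table and by the description as positives, and a program that used it would return an empty or absurd interval that would be noticed. This also stands, and it makes the sign error the more troublesome of the two, because its output looks plausible.

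A reader might infer that intervals would typically be about 40% too wide. The documents do not support that: the figure belongs to patterns with no losses, and even there one row is only 21% too wide.

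A reader might also infer that gain cannot be told from loss. SAP 8.2.1 reports counts and frequencies for both archival and de novo samples beside each change, so the direction can be recovered. Labelling the table is tidying.

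Finally, Protocol 8.2 calls the comparison hypothesis-generating, the SAP sets no decision rules, and the McNemar p values and q values do not use this formula. That limits the consequence; it does not make the formula right.

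**Conclusion.** The formula in SAP 8.1.2 is wrong as written, in two separate ways, and should be corrected. With the table's p2 and the printed signs, intervals are 21% to 41% too wide across the Table 2 settings with no losses, 1% to 17% too wide in the cases with unequal gains and losses shown above, and unchanged when gains equal losses. Taking p2 from the text makes the estimate independent of the post-progression sample.

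This rests on three assumptions. Table 2 was built with no lost alterations, which the protocol does not say but which fits every row. The R function implements the cited score method. The formula was read correctly from the PDF, which is likely because the wrong π2 and p2 agree with each other and the direction of Δ is stated twice.

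It would be going too far to conclude that Table 2 or the trial's results are wrong. Table 2 is correct under the intended method, and the exposure is confined to a macro or QC program coded from the printed text.

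**What to change.** In SAP 8.1.2:

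1. Set π2 = π11 + π21 and p2 = p11 + p21, in line with the notation table.
2. Define Δ = π2 − π1, post-progression minus archival, in both the definition and the constraint. Keep (p2 − p1) − Δ in the numerator.
3. Label the rows archival and the columns de novo.
4. Require any SAS macro to be validated against scoreci.mp() and against the Table 2 rows with whole-number counts: all rows at n = 50 and n = 100, and the 20% row at n = 75. State that these check values assume no lost alterations (b = 0). Leave out the 10% and 30% rows at n = 75, because patient-level data cannot reproduce them: 7 or 8 gains give 4.0% to 18.0% or 5.3% to 19.7%.

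The cost is a few edits to one SAP section and a short validation run. No endpoint, population, sample size or study procedure changes.
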